	
run-in period (participants will not know the identity of the study drug being administered) to obtain select baseline measurements followed by a 5 to 6 week single-blind dose titration period during which lixivaptan administered twice daily will be titrated to the highest tolerated dose. The minimum dose to enter the Double-blind, Randomized Treatment Period is 100 mg BID. Those participants successfully titrated and tolerating the study drug will then be randomized (2:1) to either continue lixivaptan or switch immediately to matching placebo in a double-blind manner. Randomization will be stratified for Chronic Kidney Disease (CKD) Stage and Mayo Clinic ADPKD Image Classification. Double-blind treatment will continue for 52 weeks after which study drug will be held, and final eGFR assessments will be obtained off-treatment during 3 follow-up visits starting on the 8th day after the last dose of double-blind study drug through the 28th day after the last dose of double-blind study drug.
 
Part 2: All participants (placebo and lixivaptan-treated) entering Part 1 will continue into Part 2 of the study and be treated with the active drug, lixivaptan, for an additional 52 weeks (following the Lixivaptan Re-titration Period) unless study drug was previously discontinued for a safety reason, or a participant withdraws consent. Assuming 90% of participants complete the Double-Blind Treatment Period (Part 1), approximately 1215 participants are projected to continue into Part 2. At the beginning of Part 2, all participants will start lixivaptan during the Lixivaptan Re-titration Period to re-establish the dose level that was tolerated during Part 1. The dose will be increased at weekly intervals until the dose level taken at the end of the Double-blind, Randomized Treatment Period in Part 1 is achieved. In order to maintain blinding of the treatment assignment from Part 1, re-titration during Part 2 will continue to be managed by the Interactive Response Technology (IRT) system.
 
Following re-titration, participants will continue on lixivaptan therapy for 52 weeks in the Maintenance Treatment Period of Part 2 and will be assessed at a study visit every 4 weeks. At the end of 52 weeks, study drug will be held, and final assessments will be obtained over 3 follow-up visits starting on the 8th day following the last dose of study drug through the 28th day after the last dose of study drug.

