8.1 Sample Size

Part 1:

Based on the results of the REPRISE trial with tolvaptan, (Torres et al, 2017) it is assumed that the standard deviation for the primary efficacy endpoint, change from baseline to post-treatment follow-up in mean eGFR, is 6.20 mL per minute per 1.73 m². Assuming a between-treatment group difference of -1.40 mL per minute per 1.73 m² and a randomization ratio of 2:1 for lixivaptan to placebo, a sample size estimate of 1314 participants (438 placebo-treated participants and 876 lixivaptan-treated participants) is required to achieve 90% power at a significance level of 0.01. In order to compensate for possible dropouts, this estimate has been adjusted up to 1350 participants (450 placebo participants and 900 lixivaptan participants). It is estimated that approximately 2250 participants will need to be screened in order to randomize 1350 participants.

A blinded sample size re-estimation (BSSR) to estimate the variance corresponding to the primary efficacy estimand is planned after at least 20% of the total randomized participants have completed Part 1 of the study or before screening for the study has ended (Section 8.2).

Part 2:

This is a convenience sample based on the number of participants who elect to continue into Part 2. It is estimated that approximately 1350 participants will be randomized in Part 1. All participants except those who discontinue due to an adverse event or withdraw consent will continue into Part 2. Approximately 90% (1215) of Part 1 participants are anticipated to continue into Part 2.

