8.3 Populations for Analysis

Part 1:

The following populations will be used for analyzing the data from Part 1:

Treated Safety Set: The Treated Safety Set consists of all participants who received at least 1 dose of study drug in Part 1.

Randomized Safety Set: The Randomized Safety Set consists of all participants in the Treated Safety Set who are randomized and receive at least 1 dose of randomized study drug.

Primary Efficacy Analysis Set (PEAS): The PEAS consists of all participants in the Randomized Safety Set who have both baseline and at least 1 valid assessment of eGFR in the Follow-up Period.

Secondary Efficacy Analysis Set (SEAS): The SEAS consists of all participants in the Randomized Safety Set who have both baseline and at least 1 on-treatment assessment of eGFR.

Part 2:

The following populations will be used for analyzing the data from Part 2:

Long-term Safety Set: The Long-term Safety Set consists of all participants in the Randomized Safety Set of Part 1 who receive at least 1 dose of lixivaptan during Part 2.

Long-term Full Analysis Set: The Long-term Full Analysis Set consists of all participants in the Long-term Safety Set who have at least 1 on-treatment measurement of eGFR in Part 2.

Long-term Efficacy Analysis Set: The Long-term Efficacy Analysis Set consists of all participants in the Long-term Full Analysis Set who were randomized to lixivaptan in Part 1.

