8.2. Primary Efficacy Analysis (Part 1)

The primary efficacy endpoint is the annualized change in eGFR (2021 CKD-EPIcr_R), with restriction as defined below, for serum creatinine from baseline (mean of 3 eGFR determinations obtained during Screening and Placebo Run-in Periods, i.e., Visits 1a (or 1b, if required), Visit 2, and Visit 3) to final assessment (mean of 3 eGFR determinations obtained during Follow-up Period I after Week 52 for on-treatment completers or, for participants who discontinue study drug treatment prior to Week 52 [Visit 22], 8 to 28 days following study drug treatment discontinuation).

Restriction refers to all annualized changes in eGFR of participants that discontinued study drug treatment that are greater (or less) than the maximum (or minimum) of the annualized eGFR change based on off-treatment serum creatinine assessments of all on-treatment completers regardless of treatment groups. For such participants, the annualized change in eGFR will assume the maximum (or minimum) value of all on-treatment completers to reduce the impact of the outliers created by the annualized eGFR change in participants that early discontinued study drug treatment.

The primary estimand for the primary efficacy endpoint is the between-treatment group difference in the change from baseline in off-treatment eGFR if all the participants in the PEAS had tolerated and adhered to their treatment for 52 weeks. Potential bias due to randomized participants prematurely discontinuing from double-blind treatment will be handled by annualizing the changes from baseline by multiplying each participant's change from baseline by 365.25 days divided by the duration from the median of the collection dates of the baseline eGFR assessments to the median of the collection dates of the 3 eGFR assessments made during the post-treatment, follow-up period immediately (8-28 days) following study drug discontinuation.

An analysis of covariance (ANCOVA) model with fixed effects for treatment group (0=placebo, 1=lixivaptan) and the randomization stratification factors (CKD stage [CKD2 versus CKD3/4] and Mayo Clinic ADPKD Image Classification [1C, 1D, or 1E]) and the baseline eGFR as a covariate.

The following SAS code will be used for the primary efficacy analysis:

```
PROC GLM ALPHA =0.01;
```

```
CLASS TREATMENT CKD_STAGE MAYO_CLASS;
MODEL ANNUALIZED_CHANGE = TREATMENT BASELINE CKD_STAGE MAYO_CLASS/SOLUTION
SS3 CLPARM;
LSMEANS TREATMENT/STDERR

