8.2.1.2. Secondary Sensitivity Analyses

Sensitivity on the annualized change in eGFR (2021 CKD-EPIcr_R) with restriction from baseline to final assessment (mean of 3 eGFR values obtained during Follow-up Period I after Week 52 for on-treatment completers or, for participants who discontinue study drug treatment prior to Visit 22, during the Follow-up Period 8 to 28 days following study drug treatment discontinuation) using a weighted ANCOVA will be performed on the PEAS. The weighted analysis is based on the reciprocal of the estimated variance of the "estimated slopes" for participants based on individual off-treatment eGFR values obtained during Follow-up Period I after Week 52 for on-treatment completers or, for participants who discontinue study drug treatment prior to Visit 22, during the Follow-up Period 8 to 28 days following study drug treatment for participants based on individual off-treatment eGFR values obtained during Follow-up Period I after Week 52 for on-treatment completers or, for participants who discontinue study drug treatment prior to Visit 22, during the Follow-up Period 8 to 28 days following study drug treatment prior to Visit 22, during the Follow-up Period 8 to 28 days following study drug treatment discontinuation). The detailed algorithm to derive the weight is provided in an Appendix.

The weighted ANCOVA model will include fixed effects for treatment group and the randomization stratification factors (CKD stage [CKD2 versus CKD3/4] and Mayo Clinic ADPKD Image Classification [1C, 1D, or 1E]) and the baseline eGFR as a covariate.

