$$\tag{2}$$

where $K_{i,0}$ is the number of eGFR observations during the pre-treatment baseline period for subject *i*, and $K_{i,j}$ is the number of eGFR observations during the post-treatment follow-up period for subject *i*, with visit *j* as the visit 22 (Week 52) for completers or mapped regular visits for early dropouts. α_i is a random variable for the "real" eGFR baseline of subject *i*, and this variable will be cancelled out for change from baseline. $\delta_{i,j}$ is a random variable for change from pretreatment baseline for subject *i* to visit *j*. These $\delta_{i,j}$ s are normally distributed, with means being $\delta_{P,j}$ for placebo subjects and $\delta_{L,j}$ for lixivaptan subjects, and variance $\sigma_{\delta,j}^2$. These $\delta_{i,j}$ s are supposed to be independent from subject to subject, and each subject has only one post-baseline visit *j* in the primary analysis. In addition, $\alpha_i s$ are assumed iid normally distributed, $e_{i,j,k}$ are assumed iid N(0, σ^2), and all these random variables are mutually independent. Their average over the $K_{i,0}$ observations at baseline and the $K_{i,j}$ observations at post-treatment follow-up will be:

$$\bar{y}_{i,0} = \alpha_i + \bar{e}_{i,0}, \qquad \text{where } \bar{e}_{i,0} \sim N(0, \, \sigma^2/K_{i,0})$$
(3)

$$\bar{y}_{i,j} = {}_{\alpha i} + \delta_{i,j} + \bar{e}_{i,j}, \qquad \text{where } \bar{e}_{i,j} \sim N(0, \ \sigma^2/K_{i,j}) \tag{4}$$

the distribution of their difference is:

$$\bar{y}_{i,j} - \bar{y}_{i,0} = \delta_{i,j} + \bar{e}_{i,j} - \bar{e}_{i,0} \sim N(., \sigma_{\delta,j}^2 + \sigma^2(1/K_{i,0} + 1/K_{i,j})),$$
(5)

where the mean of the normal distribution is $\delta_{P,j}$ for placebo subjects and $\delta_{L,j}$ for lixivaptan subjects.

In order to estimate the variance components given in (5), a further assumption of all $\sigma_{\delta,j}^2$'s are equal, ie, $\sigma_{\delta,j}^2 = \sigma_{\delta}^2$ is made, since there may not be enough subjects withdraw to stabilized the estimate of $\sigma_{\delta,j}^2$ at some visits. In addition, it is assumed all subjects get 3 eGFR observations at baseline. This assumption is reasonable, since usually subjects follow protocol schedules more strictly at the beginning of the trial and could simplify the estimation of the variance components. Then, a formula of change from baseline can be written similar to (5) for the estimation of the variance components:

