$$y_{i,j,k} - \bar{y}_{i,0} = \delta_{i,j} + e_{i,j,k} - \bar{e}_{i,0} \sim N(., \sigma_{\delta}^2 + \sigma^2(1 + 1/3)),$$
(6)

A mixed model with fixed effect factors of treatment nested within visit, replication (for the repeated observations at the post-treatment follow-up in eGFR) will be applied to change from baseline (as the average of the 3 pre-treatment eGFR observations) in eGFR observed at each replication. In this mixed model, replications at the post-treatment follow-up are considered as the repeated measurements, with a compound symmetric variance matrix structure. In this

estimated variance-covariance matrix, the diagonal elements are the estimate of $\sigma_{\delta}^2 + \sigma^2(1 + 1/3)$, and the off-diagonal elements are the estimate of $\sigma_{\delta}^2 + \sigma^2(1/3)$. Solving these two equations will get the estimates of σ_{δ}^2 and σ^2 . With these variance component estimates, the variance given in formula (5) is estimated for each subject. Dividing the estimated variance given in (5) by the subject's trial duration will provide an estimated variance for the subject's annualized change in eGFR. The inverse of this estimated variance will be the weight of the subject used in the primary analysis.

SAS code for the estimation of variance component

PROC MIXED;

CLASS USUBJID VISIT TREATMENT REPLICATION; MODEL CHANGE = TREATMENT(VISIT) REPLICATION; REPEATED REPLICATION/TYPE=CS SUB=USUBJID;

```
RUN;
```

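### The dropout step from 1314 to 1350 covers a 2.67% loss, so 90% power is not shown at the protocol's own 10% early stopping; the SAP Appendix also misplaces and misscales the weight

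*Protocol*

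**What the plan says.** **Sample size.** Protocol 8.1 assumes an SD of 6.20, a difference of 1.40, 2:1 allocation, a significance level of 0.01 and 90% power. This gives 1314 participants (438 placebo, 876 lixivaptan). It continues: "In order to compensate for possible dropouts, this estimate has been adjusted up to 1350 participants (450 placebo participants and 900 lixivaptan participants". SAP 3.7 repeats both totals but gives no reason for the increase.

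**Early stopping.** The protocol synopsis (Study Design, Part 2) states: "Assuming 90% of participants complete the Double-Blind Treatment Period (Part 1), approximately 1215 participants are projected to continue into Part 2".

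**Handling of early stoppers.** They are meant to stay in the analysis. Protocol 4.2.4 schedules three off-treatment visits after discontinuation, and protocol 8.3 admits to the primary efficacy analysis set (PEAS) those "who have both baseline and at least 1 valid assessment of eGFR in the Follow-up Period". Protocol 8.4.1 annualizes each change over the time from the median baseline date to the median follow-up date. Under SAP 8.2, an early stopper whose value falls outside the completers' range "will assume the maximum (or minimum) value of all on-treatment completers to reduce the impact of the outliers".

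**Weighting.** The primary code in SAP 8.2 reads "MODEL ANNUALIZED_CHANGE = TREATMENT BASELINE CKD_STAGE MAYO_CLASS/SOLUTION" and has no WEIGHT statement. SAP 8.2.1.2 lists a secondary sensitivity analysis "using a weighted ANCOVA will be performed on the PEAS" and sends the reader to the Appendix for the weight. The Appendix divides the variance of the change by trial duration and concludes: "The inverse of this estimated variance will be the weight of the subject used in the primary analysis".

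**Safeguard.** Protocol 8.2 plans a blinded sample size re-estimation (BSSR) that recalculates the total if the SD exceeds 6.20. SAP Section 15 removes it, citing the rise in power from 85% to 90% and projected enrolment.

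**The concern.** The increase to 1350 is the only step in 8.1 that protects power against dropout, and it is sized for about a quarter of the stopping that the protocol itself expects. Retaining early stoppers does not settle the matter. Dividing a change by a shorter time can inflate its spread, and the time before and after randomized treatment dilutes its treatment difference. In an unweighted model such values count in full.

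Three things are at stake: whether the quoted 90% can be relied on, whether the confirmatory analysis has one description, and whether anything in the plan still responds to an SD above 6.20. SAP Section 12 records early termination with 5 participants randomized, so this concerns the plan and not a result.

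**Working it through.** **1. Reproduce 1314.** Two-sided 0.01 and 90% power give z values of 2.576 and 1.282. Placebo n = (1 + 1/2) × 6.20² × (2.576 + 1.282)² / 1.40² = 437.7, so 438. With 876 on lixivaptan the total is 1314, which matches. Section 8.1 does not state sidedness; a one-sided test would give 1149.

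**2. The allowance.** 1350 − 1314 = 36, and 36/1350 = 2.67%. The synopsis figure is 1 − 1215/1350 = 10%.

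**3. All 10% lost from the PEAS.** Power = Φ(1.40/SE − 2.576), with SE = 6.20 × √(1/n₁ + 1/n₂).
- 450/900: SE 0.358, power 90.9%
- 438/876: power 90.0%
- 405/810: SE 0.377, power 87.2%

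**4. All 10% kept.** On the visit schedule, the median baseline date is about Visit 2, which is 1 + 5.5 = 6.5 weeks before randomization. The median follow-up date is about 2.6 weeks after the last dose. A completer's elapsed time is 6.5 + 52 + 2.6 = 61.1 weeks, and a Week 12 stopper's is 21.1 weeks. If the raw change has the same variance at both times, the stopper's annualized SD is 6.20 × 61.1/21.1 = 18.0. The share of the completers' difference that it carries is (12/52) × (61.1/21.1) = 0.67.

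Simulation used 12,000 trials per case (Monte Carlo error about 0.4 point), with 450/900 analysed, the cap applied and a two-sample test. These inputs are assumptions, not taken from the documents: 6.20 and 1.40 describe full-period participants, stopping is equal by arm, the difference accrues only on randomized treatment, and covariates bring no gain. Unweighted power:

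| Stopping pattern | Raw variance constant | Annualized variance ∝ 1/duration | Annualized SD constant |
|---|---|---|---|
| 10%, uniform | 80.1% | 85.3% | 89.2% |
| 10%, earlier (mean week 15) | 70.7% | 81.3% | 87.7% |
| 10%, later (mean week 35) | 85.3% | 88.2% | 90.2% |
| 5%, uniform | 85.8% | 88.3% | 89.8% |

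The first row can be checked with the step 3 formula. The simulated pooled SDs are 6.89, 6.50 and 6.20, and the mean differences 1.356, 1.364 and 1.367, which give 79.8%, 85.5% and 89.3%. With 1350 analysed and a difference of 1.40, 90% power tolerates a pooled SD of up to 1.40/(3.857 × 0.0577) = 6.29.

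**5. Design values already include early stoppers.** If 6.20 and 1.40 describe the annualized endpoint with stoppers in it and nobody is lost, power is the 90.9% of step 3.

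**6. The weight.** Var(change/T) = Var(change)/T². With equal variance of the change, a Week 12 stopper's weight relative to a completer should be (21.1/61.1)² = 0.12. Dividing by T gives 21.1/61.1 = 0.35, about 2.9 times too much.

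**The case against.** The strongest objection is to any flat statement that 1350 fails. A reader might infer from the first cell of the table that the trial has 80% power. The documents do not support that, for three reasons.

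- Section 8.1 calls 6.20 the SD of the primary efficacy endpoint, and that endpoint includes annualized early stoppers by definition. The same sentence words it as a change from baseline and does not say annualized, so the text is open. On the inclusive reading power is 90.9%.
- The equal-variance assumption is not a design assumption. The Appendix adopts it to estimate weights, "since there may not be enough subjects withdraw to stabilized the estimate of" the variance at some visits. A model with between-person slopes plus measurement noise gives about 84% to 89% under assumed noise levels.
- Uniform stopping, equal stopping by arm and no covariate gain are also assumed. Covariates would need to explain 21.9%, 11.3% or 2.0% of the variance to restore 90% in the three uniform 10% cases.

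Nor do 2.67% and 10% contradict each other as arithmetic: one concerns loss from the PEAS, the other completion of treatment.

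A reader might also infer that the SAP leaves the choice of primary analysis open, with several power points at stake (80.1% unweighted against 86.8% with the Appendix weight in the harshest uniform case). That goes too far. Protocol 8.4.1, the SAP 8.2 code and SAP 8.2.1.2 all point to an unweighted primary analysis. One Appendix sentence disagrees, and it reads as a slip.

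What stands is that the plan never connects 2.67% with 10%, never says what 6.20 and 1.40 include, and has an Appendix that conflicts with the body and misscales the weight.

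**Conclusion.** The concern holds as a gap in what the plan shows. The stated 90% is secured only up to a 2.67% loss from the PEAS. At 10% early stopping, power is 87.2% if all stoppers are lost. It is about 80% to 90% if all are kept, unweighted and capped, with uniform stopping times and the assumptions of step 4. It is 90.9% if the design values already include stoppers and nobody is lost. The documents do not allow a choice among these, so no single figure should replace 90%.

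The Appendix conflict is certain from the text, as is the need for duration squared. Neither changes the primary analysis as SAP 8.2 specifies it.

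The removed BSSR adds to the gap, because it was the plan's response to an SD above 6.20. SAP Section 15 declares the removal openly, but a higher power target does not guard against a larger SD, and protocol 8.2 still promises the step.

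**What to change.** 1. **SAP Appendix.** Say that the weight is *used in the weighted sensitivity analysis (Section 8.2.1.2)* instead of the primary analysis, and divide the variance by duration squared.
2. **Protocol 8.1 and SAP 3.7.** State that 1350 gives 90% power only up to 2.67% loss from the PEAS, and give 87.2% for 10% loss. Add the power with 10% early stoppers retained, under a written stopping pattern and variance assumption. Say whether 6.20 and 1.40 include annualized early stoppers.
3. **Protocol 8.2 and SAP Section 15.** Reconcile the two on the BSSR, and say what, if anything, now guards against an SD above 6.20.

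The cost is wording and one short power calculation. Restating the power is preferable to enrolling more. Holding 90% by enrolment would take 1314/0.90 = 1460 if all 10% were lost, or about 1377 to 1730 across the three uniform cases, and those numbers rest on assumptions the plan has not made.

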8.2 Blinded Sample Size Re-estimation

After at least 20% of the randomized participants (i.e., 270 participants) complete Part 1 of the study (Visit 25) or before screening for the study has ended, a BSSR will be performed by a blinded statistician. Based on this interim data set of blinded eGFR values, the variance corresponding to the primary efficacy estimand will be estimated and the total sample size re-estimated by a blinded statistician. If the BSSR estimates that the standard deviation of the primary efficacy estimand is less than or equal to 6.20 mL per minute per 1.73 m², then the sample size will remain at 1350 randomized participants. If the BSSR estimates that the standard deviation is greater than 6.20 mL per minute per 1.73 m², then the total sample size will be re-estimated based on this new estimate of the standard deviation by the sponsor or designee. The BSSR will be based on the original, assumed between-treatment group difference, i.e., there will be no change to the estimate of the between-treatment group difference based on the BSSR. Since a BSSR does not inflate the type 1 error of the primary efficacy analysis, the significance level for the final efficacy analysis will remain at 0.01.

8.3 Populations for Analysis

Part 1:

The following populations will be used for analyzing the data from Part 1:

Treated Safety Set: The Treated Safety Set consists of all participants who received at least 1 dose of study drug in Part 1.

Randomized Safety Set: The Randomized Safety Set consists of all participants in the Treated Safety Set who are randomized and receive at least 1 dose of randomized study drug.

Primary Efficacy Analysis Set (PEAS): The PEAS consists of all participants in the Randomized Safety Set who have both baseline and at least 1 valid assessment of eGFR in the Follow-up Period.

Secondary Efficacy Analysis Set (SEAS): The SEAS consists of all participants in the Randomized Safety Set who have both baseline and at least 1 on-treatment assessment of eGFR.

Part 2:

The following populations will be used for analyzing the data from Part 2:

Long-term Safety Set: The Long-term Safety Set consists of all participants in the Randomized Safety Set of Part 1 who receive at least 1 dose of lixivaptan during Part 2.

Long-term Full Analysis Set: The Long-term Full Analysis Set consists of all participants in the Long-term Safety Set who have at least 1 on-treatment measurement of eGFR in Part 2.

Long-term Efficacy Analysis Set: The Long-term Efficacy Analysis Set consists of all participants in the Long-term Full Analysis Set who were randomized to lixivaptan in Part 1.

